#### **Elimination criteria:**

- 1.- Subjects who during the study develop COVID-19.
- 2.- Subjects who decide to leave the study before the stipulated time for the collection of the required blood samples.

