## **General Objective**

To characterize the immunogenicity induced by COVID-19 vaccines in Mexican population: mRNA expression for IgG anti-spike.

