### **Four study groups will be formed.**

- Group 1: 20 persons who have received the Oxford/AstraZeneca vaccine (ChAdOx1 nCoV-19).
- Group 2: 20 persons who received the Gamaleya National Center vaccine (Sputnik V).
- Group 3: 20 people who have received the Pfizer/BioNTech vaccine (BNT162b2)
- Group 4: 20 persons who have received Sinovac vaccine (CoronaVac)

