### **Exclusion criteria:**

- 1.- Persons with incomplete vaccination schedule against COVID-19.

Persons who have 30 +/- 5 days after having completed the COVID-19 vaccination schedule.

- 3.- People under treatment with any immunosuppressive drug.
- 4.- Persons who refuse to sign the informed consent.

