#### **Procedure:**

(a) Participants were selected by clinical history to assess current health status, obtain demographic data, as well as personal pathological history of importance for the study (chronic degenerative diseases, history of COVID-19 disease).

b) Peripheral venous blood samples (3 ml per occasion) will be taken from all participants. They will be carried out on days 30,60 and 120 after completion of the COVID-19 vaccination schedule.

c) Sample processing:

tRNA extraction from all samples.

cDNA synthesis

Real time PCR performance.

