### **Statistical analysis**

Descriptive phase: The results were presented in tables for continuous variables with normal distribution in measurements  $\pm$  standard deviation and for free distribution in medians and percentiles. While the categorical variables were presented in percentages and total figures.

Bivariate phase: To look for differences in the quantitative variables according to the Kolmogorov-Smirnov normality test, the student t test or the Mann-Whitney U test were used or for the related ordinal variables the Wilcoxon test. The dichotomous or ordinal related qualitative variables were analyzed with the McNemar test, for the dichotomous or ordinal variables not related they were analyzed with the chi square test or Fisher's exact test.

Multivariate phase: To compare and find the differences in more than two groups in the quantitative variables with free distribution the Kruskall-Wallis test; for the related samples with free distribution the Friedman test was used. All calculations were performed using the current version of the SPSS statistical package for Windows and the Jamovi program version 4.1 of R. Statistical significance was considered to be a P value  $<0.05$  and a confidence interval of 95%.

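### Elimination is by whole subject: on its natural reading, valid samples taken before COVID-19 or withdrawal are lost from the day-30 and day-60 vaccine comparisons, mainly at a cost in precision

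*Combined protocol and SAP*

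**What the plan says.** The Elimination criteria list two grounds. The first is "Subjects who during the study develop COVID-19". The second is "Subjects who decide to leave the study before the stipulated time for the collection of the required blood samples". Both name subjects; neither mentions visits or samples already in hand.

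Four vaccine groups of 20 are planned. On blood sampling, the Procedure section says: "They will be carried out on days 30,60 and 120 after completion of the COVID-19 vaccination schedule". Its laboratory step is "tRNA extraction from all samples", which covers processing and not who is analysed.

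The General Objective is "To characterize the immunogenicity induced by COVID-19 vaccines in Mexican population: mRNA expression for IgG anti-spike". For the comparison between vaccines, the Statistical analysis section plans: "To compare and find the differences in more than two groups in the quantitative variables with free distribution the Kruskall-Wallis test". It names the Friedman test for related samples. It defines no analysis set, gives no rule for missing visits, and plans no count of eliminations, overall or by vaccine.

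**The concern.** Someone infected or withdrawing after day 60 may already have given two valid samples. If elimination removes the person, those samples go too. The analysed set at every visit is then the uninfected completers, so a day-30 result depends on what happened up to day 120.

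Setting aside samples taken after infection is reasonable, because they no longer reflect the vaccine alone. Removing samples taken before infection does nothing for that objective. The between-vaccine test does not need it either: Kruskal-Wallis can be run at each visit on whoever has a sample there.

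At stake are usable samples from groups of only 20 and, if infection risk is related to expression, some distortion of the early comparisons.

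**Working it through.** The plan gives no infection rate, dropout rate, SD or sample-size derivation, so there is no figure of its own to reproduce. The group size (20) and the visits (days 30, 60, 120) come from the document. **Every rate and odds ratio below is an assumption.**

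**1. Samples lost to infection.** Let p be the proportion of a group infected between days 30 and 120, at constant hazard h = −ln(1 − p)/90. Then p1 = 1 − exp(−30h) are infected in days 30–60 and p2 = exp(−30h) − exp(−90h) in days 60–120. Whole-subject removal loses 20p valid day-30 samples and 20·p2 valid day-60 samples. It leaves 20(1 − p) people at every visit. Cutting at the event leaves 20 at day 30 and 20(1 − p1) at day 60.

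| p | 5% | 10% | 20% |
|---|---|---|---|
| p1 | 0.0170 | 0.0345 | 0.0717 |
| p2 | 0.0330 | 0.0655 | 0.1283 |
| Day-30 samples lost per group | 1.0 | 2.0 | 4.0 |
| Day-60 samples lost per group | 0.7 | 1.3 | 2.6 |
| Analysed at every visit, subject removed | 19 | 18 | 16 |
| Analysed at day 60, cut at event | 19.7 | 19.3 | 18.6 |
| SE ratio, day 30: √[1/(1 − p)] | 1.026 | 1.054 | 1.118 |
| SE ratio, day 60: √[(1 − p1)/(1 − p)] | 1.017 | 1.036 | 1.077 |

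The SE ratios are for a difference of two means with equal loss in both groups, used here as a guide to the rank test. Day 120 is the same under either rule.

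**2. Samples lost to withdrawal.** With a fraction q retained per interval, 20(1 + q + q²) samples per group are collected and 60q² survive complete-case removal. For q = 0.95, 0.90 and 0.85 the loss is 57.05 − 54.15 = 2.9, 54.2 − 48.6 = 5.6 and 51.45 − 43.35 = 8.1 samples per group.

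**3. Dependence on day 30.** The Exclusion criteria list "Persons who have 30 +/- 5 days after having completed the COVID-19 vaccination schedule", which as written conflicts with a day-30 sample. If no day-30 samples exist, the infection loss is 0.7, 1.3 or 2.6 per group. The withdrawal loss is then 20(q + q²) − 40q² = 0.95, 1.8 or 2.55.

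**4. Bias in a vaccine contrast from the infection criterion.** Take expression as N(μ, 1), with a true difference of 1 SD between two vaccines and equal exposure. Infection risk is logistic in expression, with an odds ratio (OR) per SD of higher expression and a common intercept set so that 5%, 10% or 20% of the stronger group are infected. The mean among the uninfected is found by numerical integration, and SE = √(1/n1 + 1/n2) with the retained numbers.

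| OR per SD | Infected, weaker group | Observed contrast (SD) | Bias/SE |
|---|---|---|---|
| 1 | 5 / 10 / 20% | 1 / 1 / 1 | 0 / 0 / 0 |
| 0.7 | 7.0 / 13.6 / 26.2% | 0.993 / 0.987 / 0.979 | 0.02 / 0.04 / 0.06 |
| 0.5 | 9.3 / 17.6 / 32.1% | 0.972 / 0.952 / 0.926 | 0.09 / 0.14 / 0.20 |

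Worked case, OR 0.5 with 20% infected in the stronger group: n1 = 16, n2 = 20 × 0.679 = 13.6, SE = √(1/16 + 1/13.6) = 0.369, and bias = (1 − 0.926)/0.369 = 0.20 SE. Both retained means shift upward, and much of the shift cancels in the contrast.

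**The case against.** **Elimination may mean only that participation stops.** The text never says that samples already taken are discarded, and extraction is planned for all samples. This stands in part: a reader might infer that the plan expressly orders deletion, and it does not. But nothing keeps the earlier samples either, and the criteria name subjects. Two analysts could build different data sets from this plan.

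**The effect is small.** This stands. A reader might infer that the vaccine comparison is seriously biased by selection. The documents support no such claim: they state no link between expression and infection risk and give no rates. In the model above, a bias near half a standard error (0.46) needs an odds ratio of 0.3 and about 40% of the weaker group infected within 90 days. Unequal exposure between groups could move the contrast either way.

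**The Friedman test needs complete series anyway.** This stands. The gain is confined to the between-vaccine comparisons at days 30 and 60.

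**Withdrawers' samples may be governed by consent.** This stands. The consent pages were not available for review, so the withdrawal criterion carries less weight than the infection criterion.

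**Nothing forbids a table of eliminations.** True. Its absence is missing detail, not concealment, and does not carry the point.

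**Conclusion.** The point holds as a minor one. As naturally read, the rule drops valid pre-event samples and makes the early vaccine comparisons conditional on later events, with no benefit to the stated objective. At an assumed 5–20% infected, the standard error is about 3–12% larger at day 30 and 2–8% larger at day 60. Contrast bias runs from zero to about 0.2 SE for odds ratios between 1 and 0.5. The day-30 part rests on day-30 samples being taken, so the Exclusion criteria and the Procedure section must be reconciled separately.

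A reader might also infer that keeping the samples would let the study test its re-contagion hypothesis. It would not: no infection testing is scheduled, and counts out of 20 are very imprecise (exact 95% CI 0–16.8% for 0/20 and 1.2–31.7% for 2/20).

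**What to change.** Reword the Elimination criteria along these lines: *if a participant develops COVID-19 or withdraws, samples from onset or withdrawal onward are left out of the main analysis; earlier samples are kept, those of withdrawn participants only as their consent allows.*

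Then:

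- Use the kept samples in the between-vaccine Kruskal-Wallis comparison at each visit. Leave the Friedman test on complete series.
- Flag samples taken within the 5–7 day incubation period (given in the COVID-19 section) before onset, and check that the result holds without them. Few are expected: with a 7-day window, 20[1 − exp(−7h)] is about 0.08 to 0.34 per group per visit at 5–20% infected.
- Report the numbers enrolled, infected, withdrawn and analysed, by vaccine and visit.
- Show post-infection samples separately, and only if they were collected anyway.

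The cost is a rewording of two criteria, one table and one check, with no added participants or visits. The downsides are that numbers will differ by visit and infection counts will rest on reported cases. The change removes dependence on later events but not all selection: day-60 and day-120 values will still come from people uninfected and attending up to that visit.

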#### **Procedure:**

(a) Participants were selected by clinical history to assess current health status, obtain demographic data, as well as personal pathological history of importance for the study (chronic degenerative diseases, history of COVID-19 disease).

b) Peripheral venous blood samples (3 ml per occasion) will be taken from all participants. They will be carried out on days 30,60 and 120 after completion of the COVID-19 vaccination schedule.

c) Sample processing:

tRNA extraction from all samples.

cDNA synthesis

Real time PCR performance.

#### **Ethical Aspects**

The present study will strictly follow the ethical norms for research established in the Declaration of Helsinki, at the international level. This Declaration suggests that the sole purpose of research in humans should be the improvement of diagnostic, therapeutic and prophylactic methods, as well as the understanding of the etiology and pathogenesis of diseases. At the national level, according to article 17 of the Regulations of the General Health Law on Health Research, this study is considered of minimal risk for the participants, since 3mL of blood will be taken by venous

puncture. Individuals who wish to participate will be asked to sign the specific informed consent form, after a thorough explanation of the procedure.

The data obtained from the individuals participating in the study will be protected by the "Federal Law for the protection of personal data", so the anonymity of the samples and the participants is guaranteed. The results of the study will be under the custody and responsibility of the principal investigator for subsequent analysis and publication in scientific journals.

### Schedule

Stage 1	Stage 2	Stage 3
Sample collection	Experimental	Analysis of results and re writing.
Duration: 4 months (September December 2021)	Duration: 4 months (January-February 2022)	Duration: 3 months (May-2022)

Collection and transport of bl samples from all selected participants.
 
✓ Extraction of tRNA from bl samples.
 
✓ cDNA synthesis.
 
✓ Real-time PCR.
		

### **Statistical analysis**

Descriptive phase: The results were presented in tables for continuous variables with normal distribution in measurements  $\pm$  standard deviation and for free distribution in medians and percentiles. While the categorical variables were presented in percentages and total figures.

Bivariate phase: To look for differences in the quantitative variables according to the Kolmogorov-Smirnov normality test, the student t test or the Mann-Whitney U test were used or for the related ordinal variables the Wilcoxon test. The dichotomous or ordinal related qualitative variables were analyzed with the McNemar test, for the dichotomous or ordinal variables not related they were analyzed with the chi square test or Fisher's exact test.

Multivariate phase: To compare and find the differences in more than two groups in the quantitative variables with free distribution the Kruskall-Wallis test; for the related samples with free distribution the Friedman test was used. All calculations were performed using the current version of the SPSS statistical package for Windows and the Jamovi program version 4.1 of R. Statistical significance was considered to be a P value  $<0.05$  and a confidence interval of 95%.

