## **Problem Statement**

The precise mechanism by which a vaccinated patient has a high probability of being infected with a different strain of SARS-CoV-2 is currently unknown. Assuming this, recontagion and further increases in the rates of active cases of COVID-19 in the vaccinated population are not prevented. Therefore, by determining the molecular mechanisms of infection, therapeutic targets can be identified, and specific treatments can be offered to prevent infection in both first-contact subjects and those with a history of COVID-19 infection.

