## **Hypothesis**

Gene expression for IgG anti-spike in subjects with a complete vaccination schedule against COVID-19 does not develop the necessary immunogenicity in the Mexican population to prevent re-contagion.

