## **Methodology**

Type of study, general design and population

A quasi-experimental, longitudinal, retrospective, comparative, quasi-experimental study will be carried out in a Mexican population older than 18 years with a complete vaccination schedule against COVID-19, to determine the immunogenicity induced by the vaccines.

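### Groups are formed by vaccine already received and every between-group test is unadjusted, so a difference cannot be attributed to the vaccine if prior COVID-19 or age is unevenly spread

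*Combined protocol and SAP*

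**What the plan says.** The Methodology section describes the design: "A quasi-experimental, longitudinal, retrospective, comparative, quasi-experimental study will be carried out in a Mexican population older than 18 years". Four groups of 20 are then formed according to which of four vaccines a person has had. No randomisation, matching or stratification is described.

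The inclusion criteria set a lower age limit and no upper one. The exclusion criteria do not mention COVID-19 before enrolment, and the elimination criteria remove only people who develop it during the study.

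The Procedure section states "Participants were selected by clinical history to assess current health status", and goes on to "obtain demographic data, as well as personal pathological history of importance for the study (chronic degenerative diseases, history of COVID-19 disease". It does not say how that history was used in selection. On blood sampling it says "They will be carried out on days 30,60 and 120 after completion of the COVID-19 vaccination schedule", so there is no sample from before vaccination.

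The between-group tests named in the Statistical analysis section are Student t, Mann-Whitney, chi-square, Fisher and, in the Multivariate phase, "To compare and find the differences in more than two groups in the quantitative variables with free distribution the Kruskall-Wallis test". The only other test in that phase is Friedman, for related samples. Significance is set at P below 0.05.

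**The concern.** People who received different vaccines may differ in age and in earlier infection. Nothing in the eligibility criteria prevents this, and nothing in the analysis corrects for it. The protocol itself treats these variables as relevant, since it collects them, but no planned analysis of expression uses them. Chi-square or Fisher tests on the collected items would at most describe an imbalance.

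Two other places suggest that previously infected people are in scope. The Problem Statement refers to preventing infection "in both first-contact subjects and those with a history of COVID-19 infection", and the Hypothesis is that the response "does not develop the necessary immunogenicity in the Mexican population to prevent re-contagion".

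What is at stake is interpretation. The General Objective is "To characterize the immunogenicity induced by COVID-19 vaccines in Mexican population", and the study is called comparative. A significant Kruskal-Wallis result would naturally be read as one vaccine inducing more expression than another, when the cause could be infection history or age. With no pre-vaccination sample, change from baseline is not available as a remedy.

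**Working it through.** **The plan's own figures.** The documents give no effect size, SD, prevalence, age distribution or sample-size calculation, so there is nothing to reproduce. From the documents come four groups, 20 per group and the 0.05 level. Two-sided testing and every prevalence, age and effect below are assumptions.

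**Step 1: size of the spurious difference.** With no vaccine effect, let expression be y = d·x + b·age + e, where x is prior infection (0/1) and e has SD 1. The expected difference between two groups is

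d × (difference in prevalence) + b × (difference in mean age).

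- Prevalence 20% vs 35%, d = 1: 1 × 0.15 = 0.15 SD.
- Prevalence 10% vs 50%, d = 1: 1 × 0.40 = 0.40 SD.
- Mean ages 15 years apart, slope 0.02 SD per year: 0.02 × 15 = 0.30 SD.
- The last two together: 0.40 + 0.30 = 0.70 SD in the same direction, or 0.40 − 0.30 = 0.10 SD if they oppose.

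**Step 2: false-positive rate of the planned tests.** Simulation, normal outcome, no vaccine effect, 10,000 replicates. Kruskal-Wallis is used except in the two-group row (Mann-Whitney).

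| Prior infection by group | d = 0.5 | d = 1 | d = 1.5 |
|---|---|---|---|
| 30% in all four | 4.4% | 4.6% | 4.7% |
| 20/25/30/35% | 5.2% | 6.3% | 6.8% |
| 10/20/40/50% | 7.3% | 14.9% | 26.5% |
| 10% vs 50% (two groups) | 9.1% | 20.2% | 35.0% |

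| Mean age by group (within-group SD 12) | 0.01 SD/year | 0.02 SD/year | 0.03 SD/year |
|---|---|---|---|
| 44/46/48/50 | 4.8% | 5.6% | 6.6% |
| 40/45/50/55 | 5.9% | 9.9% | 17.4% |

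| Both: 10/20/40/50% and ages spread over 15 years | d = 0.5, 0.01/year | d = 1, 0.02/year | d = 1.5, 0.03/year |
|---|---|---|---|
| Same direction | 13.3% | 37.0% | 62.8% |
| Opposing | 5.4% | 5.6% | 6.5% |

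A separate simulation with 4,000 replicates gave 14.7% for 10/20/40/50% at d = 1 and 5.0% when prevalence was equal.

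**Step 3: the same data with adjustment.** A linear model with vaccine and fully recorded covariates gives 4.5% to 5.3% in every scenario, as it must by construction. A rank-based analysis of covariance in the separate simulation gave 4.2% to 6.0%.

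If clinical history misses half of infections, the adjusted rates (d = 0.5/1/1.5) are:

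- 10/20/40/50%: 6.1 / 9.2 / 13.2%.
- 10% vs 50%: 6.8 / 11.6 / 18.4%.
- Opposing age and infection: 6.2 / 8.0 / 11.8%, which is worse than the unadjusted 5.4 / 5.6 / 6.5%.

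**Step 4: would a baseline test reveal the imbalance?** Power for two proportions at n = 20 per group, with pooled proportion p:

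power = Φ{[|p1 − p2| − 1.96·√(2p(1−p)/n)] / √([p1(1−p1) + p2(1−p2)]/n)}

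- 10% vs 40%: Φ[(0.30 − 1.96 × 0.1369)/0.1285] = Φ(0.246), about 60%.
- 20% vs 40%: Φ[(0.20 − 1.96 × 0.1449)/0.1414] = Φ(−0.594), about 28%.

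A non-significant baseline test would therefore not show balance.

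**The case against.** The documents do not show that either covariate affects the outcome. The introduction links infection to neutralizing antibodies only when discussing the M protein, and links age only to disease severity. Neither statement concerns anti-spike IgG mRNA. Support for age is weaker than for prior infection, because the phrase about importance is attached to pathological history while age falls only under demographics. This stands, and it is why the conclusion is conditional.

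The hypothesis and objectives name no vaccine-against-vaccine contrast, and the Statistical analysis section does not say which variable Kruskal-Wallis will compare. This also stands. But the study is called comparative, has four vaccine groups and plans a test for more than two groups. The Friedman, Wilcoxon and McNemar comparisons are within-person, so fixed characteristics do not confound them in the same way, and they are not criticised here.

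Previously infected people may have been screened out through clinical history without this being written down. That is possible. If so, the criterion needs to be stated, and age remains.

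The large error rates need a strong imbalance and a strong effect. Under modest imbalance the error stays near nominal. Adjustment is also imperfect, because history misses asymptomatic infection, and it can do harm when biases happen to cancel. All of this is true. It argues for reporting adjusted and unadjusted results side by side, and for naming one primary model so that analyst choice is not left open. It does not argue for leaving adjustment out.

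**Conclusion.** The concern holds. The groups are not randomised, and no between-group test in the plan uses the covariates that the protocol collects. A significant difference between vaccine groups could reflect infection history or age instead of the vaccine.

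The direction and size of any bias are unknown and may be negligible. In the illustration, the nominal 5% error is barely changed under modest imbalance (5.2 to 6.8% for prior infection). It reaches 26.5% for 10/20/40/50% at 1.5 SD and about 63% if age reinforces it. These rates rest on assumed prevalences, ages and effects, a normal outcome and all 20 per group retained. The missing adjustment is certain; its consequence is conditional. It should be fixed because the remedy is cheap and the between-vaccine result is hard to interpret without it.

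**What to change.** In the Statistical analysis section, add one between-vaccine analysis named as primary before the data are analysed. A suitable choice is a mixed model of suitably transformed expression with vaccine, day (30, 60, 120), vaccine-by-day, age, prior COVID-19 (yes/no) and a subject random effect. Add chronic disease only if numbers allow. A regression at each sampling day with the same covariates is a simpler alternative.

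- State in advance how expression is quantified and transformed, and how undetected values are handled.
- If no transformation is suitable, use a rank-based test stratified by prior COVID-19, with undetected values sharing the lowest rank. This does not deal with age unless an age band is added as a stratum.
- Report adjusted differences with 95% confidence intervals, and keep Kruskal-Wallis as the unadjusted analysis.
- Show a baseline table by vaccine, and repeat the analysis in people without known prior COVID-19.
- In the Procedure section, confirm that age is recorded and state how clinical history was used in selection. If prior COVID-19 was in fact excluded, list it in the exclusion criteria and adjust for age only.
- Describe between-vaccine contrasts as associations. Label the adjusted analysis post hoc if any analysis has already been run.

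**Cost.** SAP wording and a small analysis of data already planned for collection. For an assumed 0.8 SD shift in one of four balanced groups, power of the linear model falls from 70.8% to 69.4% with two covariates (68.9% with three) if they do not matter. If they do matter (1 SD and 0.02 SD per year), it rises from 60.0% to 70.1% with two. Losses under the elimination criteria would lower power with or without adjustment: at an assumed 16 per group, adjusted power is about 58%. Before such losses, the restricted analysis keeps 20 × (0.9 + 0.8 + 0.6 + 0.5) = 56 of 80 at 10/20/40/50%, or 20 × (0.8 + 0.75 + 0.7 + 0.65) = 58 at 20/25/30/35%. Residual confounding will remain.

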## **Specific objectives**

1. Determine the mechanisms of virus transmission on the cell.
2. To identify the study population.
3. To identify the anti-spike IgG genes in vaccinated population.

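### Four vaccines sampled on three days are compared only with one-factor, two-sample or paired tests at P<0.05: no primary comparison, no multiplicity rule, and no specified between-vaccine test of change

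*Combined protocol and SAP*

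**What the plan says.** Methodology describes the design: "A quasi-experimental, longitudinal, retrospective, comparative, quasi-experimental study will be carried out". It lists four vaccine groups of 20. Procedure, item (b), samples everyone on days 30, 60 and 120 after the schedule is complete.

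The Statistical analysis section is the whole analysis plan. For quantitative outcomes it names:

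- Bivariate phase, after a Kolmogorov-Smirnov check: "the student t test or the Mann-Whitney U test were used or for the related ordinal variables the Wilcoxon test".
- Multivariate phase, across groups: "To compare and find the differences in more than two groups in the quantitative variables with free distribution the Kruskall-Wallis test".
- Multivariate phase, across repeated samples: "for the related samples with free distribution the Friedman test was used".
- Threshold: "Statistical significance was considered to be a P value" below 0.05. A 95% confidence interval is mentioned, but for no named estimate.

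The aims do not narrow this down. The General Objective is "To characterize the immunogenicity induced by COVID-19 vaccines in Mexican population: mRNA expression for IgG anti-spike". A specific objective is "To identify the anti-spike IgG genes in vaccinated population". The Hypothesis is that anti-spike IgG gene expression "does not develop the necessary immunogenicity in the Mexican population to prevent re-contagion". None of them says whether the level on one day or the change over time is the main question.

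**The concern.** Vaccine and day are both factors in this design, yet every listed test handles one factor, two samples or one pair. Three things follow.

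- **Which result counts is open.** Three days and six vaccine pairs offer many comparisons at 0.05. A reader of the results could not tell a planned vaccine difference from a selected one.
- **The normal branch has no four-group test.** Kruskal-Wallis and Friedman are reserved for non-normal data. If expression passes the check, only the two-sample t test remains for comparing four groups, and no test is named for three related samples.
- **Change is not compared between vaccines.** Friedman asks whether days differ within related samples. It does not ask whether vaccines differ. The study is called longitudinal and comparative, but no test is specified for that combination.

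**Working it through.** The plan states no power, effect size or error-rate figure, so there is none to reproduce.

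**Inputs from the documents.** 4 groups, n = 20 each, 3 days, threshold 0.05.

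**Assumptions.** Normal, complete data; equal correlation ρ between days, 0.3 to 0.7; differences d in SDs of a single-day measurement.

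**1. Number of between-vaccine comparisons.** Pairs: 4 × 3 / 2 = 6. Over three days: 6 × 3 = 18.

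**2. Chance of at least one false vaccine difference** (simulated, no true differences, 20,000 replicates):

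| Use of the tests | ρ = 0.3 | ρ = 0.5 | ρ = 0.7 |
|---|---|---|---|
| Non-normal branch: Kruskal-Wallis on three days | 13.3% | 12.5% | 11.1% |
| Non-normal branch: Mann-Whitney pairs only after a significant Kruskal-Wallis | 13.3% | 12.5% | 11.1% |
| Non-normal branch: 18 ungated Mann-Whitney tests | 47.2% | 44.2% | 39.7% |
| Normal branch: six ungated t tests, one day | 20.6% | 20.3% | 20.5% |
| Normal branch: 18 ungated t tests | 47.2% | 43.9% | 39.0% |
| One pre-named Kruskal-Wallis, one day's level | 4.7% | 4.8% | 4.8% |
| One pre-named Kruskal-Wallis, day 30-to-120 change | 4.8% | 4.9% | 4.5% |
| Holm over six t tests, one day | 4.2% | 4.1% | 4.0% |

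A repeat run put the 18 t tests at 40-48%, hence about 39-48% overall. On any one day, a rank test's null rate does not depend on the shape of a continuous distribution. The normal-data simulation can therefore stand for the non-normal branch; the correlation remains an assumption.

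**3. Can separate Friedman tests stand in for a comparison of change?** All four vaccines were given the same decline (assumed 0.3 to 0.7 SD by day 120, ρ = 0.5 or 0.7; 4,000 runs per setting). Friedman was significant in some vaccines but not others in 44-86% of runs. Kruskal-Wallis on each person's change rejected in 4.6-5.1%.

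**4. Power of a specified test of change.** One vaccine's day 30-to-120 change differs by d.

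- *3-df contrast, vaccine × (day 120 minus day 30).* Noncentrality λ = n × 0.75d² / [2(1−ρ)], with 3 and 2(4n−4) df. For n = 20, d = 0.8, ρ = 0.5: λ = 20 × 0.75 × 0.64 / 1 = 9.6 on 3 and 152 df, power 73%.
- *6-df vaccine × day term, difference growing linearly.* The profile is 0, d/3, d, because (60−30)/(120−30) = 1/3. The squared deviations from its mean sum to (42/81)d², so λ = n × 0.75 × (42/81)d² / (1−ρ). With the same inputs λ = 9.96 on 6 and 152 df, power 62%.

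| Power at d = 0.5 / 0.8 / 1.0, ρ = 0.5 | n = 20 | n = 16 |
|---|---|---|
| 3-df contrast | 33 / 73 / 91% | 27 / 62 / 83% |
| 6-df term, linear growth | 25 / 62 / 84% | 20 / 50 / 73% |
| Kruskal-Wallis on change | 30 / 69 / 88% | 24 / 57 / 79% |
| Kruskal-Wallis on one day's level | 30 / 68 / 88% | 24 / 56 / 78% |

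If the full difference is already present by day 60, the 6-df term has 32 / 75 / 93% at n = 20. Its power therefore depends on a day-60 pattern that the documents do not give. n = 16 represents an assumed 20% loss; the documents state no loss rate.

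**5. Price of adjusting six pairs on one day.** Noncentral t, 80% power, 0.05 against 0.05/6: the detectable difference rises from 0.91 to 1.15 SD at n = 20, and from 1.02 to 1.31 SD at n = 16. These are Bonferroni bounds, and Holm is no worse. If one vaccine differs by 0.8 SD (n = 20, 40,000 replicates), the true pairs flagged fall from 2.1 to 1.3 of 3, and the chance of any false pair falls from 12% to 3%.

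**The case against.** The study is small, its general objective is to characterize, and no vaccine is hypothesised to be better. A full confirmatory framework can look out of proportion. This stands in part: declaring every test exploratory and reporting estimates with intervals is a legitimate repair. The plan does not do that. It sets a significance threshold, looks for differences among more than two groups and labels nothing exploratory.

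The listed tests are also not incapable of comparing change. Kruskal-Wallis applied to each person's change would do so. This stands too: the gap is in specification, because the plan never says the test will be used that way.

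A reader might infer three stronger things, and the documents support none of them.

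- *That the plan's error rate is 39-48%.* That needs all 18 pairwise tests to be run ungated. The plan does not say so, though it does not exclude it. Treating the 18 as independent would give 1 − 0.95^18 = 60%, which overstates the risk because the tests are correlated.
- *That the investigators will read separate Friedman results as vaccine differences.* Nothing says they will. The warning is needed only because no other comparison of change is specified.
- *That a vaccine × day interaction is automatically the right replacement.* With three categorical days it spends 6 df. Under steady divergence it has less power than the 3-df contrast.

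**Conclusion.** The concern holds and the plan should be changed. For four groups and three days it names no primary comparison, no multiplicity rule and no between-vaccine test of change, and it has no four-group test for data that pass the normality check.

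The size depends on the branch. It is 11-13% for Kruskal-Wallis on three days in the non-normal branch, and 20-21% for six ungated t tests on a single day in the normal branch. It reaches about 39-48% only if all 18 pairs are tested without a gate. One pre-named four-group test brings it to about 5%. These rates rest on complete data and between-day correlations of 0.3 to 0.7, which are assumptions and not figures from the documents. The gaps themselves can be read directly from the Statistical analysis section and rest on no assumption.

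**What to change.** 1. **Name one primary between-vaccine comparison, or declare none.** The sponsor chooses between the level on one named day and the day 30-to-120 change. Test it with one four-group test whatever the normality check shows: Kruskal-Wallis, or a one-way or mixed model on log expression (an assumed scale; Procedure, item (c), defines none). Alternatively, label every test exploratory, drop claims of significance and report estimates with 95% intervals.
2. **In either case, specify a between-vaccine test of change.** Use Kruskal-Wallis on each person's day 30-to-120 change, or the 3-df vaccine × (day 120 minus day 30) contrast in a mixed model, not the 6-df vaccine × day term. Do not read separate Friedman results as vaccine differences.
3. **If a primary is named**, report its six pairwise contrasts with Holm-adjusted P values and simultaneous intervals, or state that the 95% intervals are unadjusted and may disagree with the Holm result. Label all other tests exploratory.

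**Cost.** No extra samples: a few sentences of analysis text and a definition of the expression scale. The price is fewer nominally significant pairs and only modest power for change, as shown in the working. Choosing a single-day level as primary does not avoid the modest power.

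**Separate points to reconcile before any endpoint uses day 30.**

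- Exclusion criteria excludes people by reference to 30 ± 5 days after the schedule, while Procedure takes a sample on day 30.
- Elimination criteria does not say whether people who are removed contribute their earlier samples.
- Schedule gives September to December 2021 for collection, at most 30 + 31 + 30 + 31 = 122 days. A change over 120 − 30 = 90 days that ends by 31 December needs a first sample by 2 October.
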